MEASURES. Parents and teens will complete a baseline assessment either immediately after providing informed consent / assent or shortly thereafter via phone or video conference by Brown University staff. Follow-up measures will also be conducted by phone or video conference by Brown University staff at 6, 12, and 24 weeks following the teen's discharge. The baseline assessment will be about 1.5 hours for the adolescent and 1 hour for the parent and the follow-up assessments will be about 1.5 hours for both the adolescent and parent. Parents and adolescents have been able to complete assessments of this length or longer in our team's prior and current studies.

The measures used in this study are outlined below. Based on our team's experience working with 100s of families on clinical research projects in Rhode Island, we have decided to translate all of the **parent** measures into Spanish. We retain all of the adolescent measures in English. It is well established that adolescents tend to acculturate to the U.S. culture more quickly than their parents, and we have found that adolescents in our studies from Spanish-speaking families are typically comfortable speaking and completely measures in English or Spanish, while parents tend to prefer to speak in Spanish. If adolescents prefer to speak in Spanish, we will use a translator to administer all of the adolescent measures aloud.

Rationale for Measures: Aim 1. To address Aim 1, we will assess feasibility and acceptability.

Feasibility. PW feasibility will be assessed based upon the percent of parents willing to participate as well as indicators of parental engagement, including: number of coaching sessions attended before teen's discharge, number of coaching sessions attended after discharge, number of PW logins, number of PW online sessions completed, amount of time spent logged into PW program, number of logins to the parent message board, number of questions posted to the message board, and amount of time spent logged into the board.

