By using the GAIN at follow-ups, we will capture continuous data on the teen's use and high-risk behaviors following discharge. We will also include measures of parental communication and monitoring (Aim 4), as these outcomes are not included in the GAIN and parenting practices are a key factor associated with ASUD. PI [name] is a certified GAIN trainer and has experience analyzing GAIN data. Specific scales that we will analyze to address Aims 2 and 3 are described below.

Demographics. The GAIN Background section collects routine socio-demographic variables including age, sex, ethnicity, race, and grade in school. Items in other GAIN sections indicate the teen's history of substance use or mental health treatment utilization, data that will be used to control for additional treatment received.

Substance Use. The following GAIN items/scales and biological markers will address Aim 2 (substance outcomes).

Days of Use (Past 90 Days). A series of GAIN items evaluate days of substance use over the past 90 days. These items have shown excellent comparability to the well-validated Timeline Follow-Back Interview (TLFB). Like the TLFB, the GAIN assesses days of alcohol and drug use using a calendar with temporal cues (e.g., holidays, special events) to facilitate recall. We will analyze three variables, separately for alcohol, marijuana, and other drugs: total number of use days, total days abstinent, and latency to first use.

Substance Frequency Scale (SFS). The SFS scale averages the percent of days in the past 90 during which there was use of alcohol, marijuana, or heavy drugs; use to intoxication; and failure to perform activities due to use. This scale has good reliability ($\alpha = .85$) and predicts substance-related problems as well or better than biometric (e.g., urine) markers of use.

Biological markers. Biological markers will **only be used at the follow-up assessments (6, 12, and 24 weeks)**, since adolescents are not expected to have access to substances at the time of the baseline assessment (likely to be at least 1-2 days after admission). 8-panel urine screens that detect the presence of marijuana, cocaine, amphetamines, methamphetamines, MDMA, opiates, oxycodone, and benzodiazepines mailed to each family and administered to the teens by the parents will be used to provide a biological indicator of abstinence. Teens who present as acutely intoxicated based on researcher observations, parent-report, or adolescent-report will be rescheduled.

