We will begin by comparing the DV scores (means of continuous DVs and percentages of categorical DVs) at each assessment. We will conduct separate mixed models predicting each DV by condition, controlling for the following covariates: baseline status on the DV, baseline differences between groups, and any mental health or substance use treatment received over the follow-up period. We will analyze the effect of PW dosage on each DV and calculate partial eta squared (η^2) to estimate the proportion of variance caused by PW. We are underpowered to test mediation, but will examine the effects of PW on our putative mediators (Aim 4), and correlations between change in the mediators and change in the primary outcomes (Aims 2-3), with the goal of finding promising trends to pursue in a larger trial. We will cautiously attempt more sophisticated analyses using hierarchical modeling, a flexible approach to analyzing change that has been frequently used by the PI [37, 90, 91]. Mixed models are ideally suited to address Aims 2-4, by enabling us to compare the conditions at each time point while accounting for the correlation of observations over time. Although convergence is challenged in a small sample, it is feasible. Our primary goal will be to provide measures of association and 95% confidence intervals to reveal the ES of PW on each DV.

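### Latency to first use has no stated time origin or rule for teens who have not used, and on its most natural reading the mixed model planned for every outcome does not fit it

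*Combined protocol and SAP*

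**What the plan says.** Section C.2, Measures, Days of Use (Past 90 Days), introduces the instrument with "A series of GAIN items evaluate days of substance use over the past 90 days" and names three variables to be analysed for alcohol, marijuana and other drugs: "total number of use days, total days abstinent, and latency to first use". It does not say from what day latency is counted, what value an abstinent teen receives, or how the three follow-up interviews are combined.

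The Data Analysis Plan (Aims 2 - 4) starts by "comparing the DV scores (means of continuous DVs and percentages of categorical DVs) at each assessment". It continues: "We will conduct separate mixed models predicting each DV by condition", "controlling for the following covariates: baseline status on the DV", followed by baseline group differences and treatment received during follow-up. The stated aim of these analyses is: "Our primary goal will be to provide measures of association and 95% confidence intervals to reveal the ES of PW on each DV". Latency is not excepted, and no censored-data method appears anywhere.

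Three places point to discharge as the clock. Follow-up interviews take place "6, 12, and 24 weeks following the teen's discharge". The follow-up interview is meant to capture "use and high-risk behaviors following discharge". The analysis section restricts trajectories to the follow-up period.

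**The concern.** Counted from discharge, first use of a class happens at most once per teen. A teen who stays abstinent or is lost has a right-censored time. Nothing measured at baseline is the same quantity, so the baseline covariate does not exist. With one row per teen, a random intercept cannot be separated from residual error. The plan's general provisions do not help: no transformation supplies an unobserved event time, and the multiple imputation is meant for unplanned missingness, whereas a teen who is abstinent at week 24 has been fully observed.

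The analyst would therefore have to invent a coding after the data are in. The plausible codings give different effect sizes, and the plan intends to use its effect sizes to size a larger trial.

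**Working it through.** **Plan's own figures.** The plan gives no figure for latency. Its allowance of 15-20% loss from 60 leaves 51 to 48, consistent with its 50, so 25 per arm is used below. It gives no relapse rate either, so the rates here are assumptions.

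**1. Recall windows relative to discharge** (interview day minus 90):
- week 6: 42 − 90 = −48, so day −48 to 42
- week 12: 84 − 90 = −6, so day −6 to 84
- week 24: 168 − 90 = 78, so day 78 to 168

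Together they cover days 0-168, so one discharge-to-first-use time per teen and class can be built. If the 12-week interview is missed, days 42 to 78 are not covered. If latency is instead counted within each window, it has a baseline value, but the first window opens 48 days before discharge and the last opens 78 days after it. The three values are not the same post-discharge quantity.

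**2. Latency capped at each visit.** Assume exponential time to first use with rate λ. The restricted mean to day t is R(t) = (1 − e^(−λt))/λ. Take a usual-care median of 84 days (λ = ln 2/84 = 0.00825) and a hazard ratio of 0.5 (λ = 0.00413).

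| Day | Usual care | PW | Difference |
|---|---|---|---|
| 42 | 35.49 | 38.56 | 3.1 |
| 84 | 60.59 | 70.99 | 10.4 |
| 168 | 90.89 | 121.19 | 30.3 |

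Average of the three differences: 14.6. For usual-care medians of 42/84/168 days, the pooled average against the day-168 difference is 18.1/14.6/9.5 against 34.1/30.3/20.8 at hazard ratio 0.5, and 9.5/8.1/5.5 against 17.3/16.6/11.9 at 0.7.

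**3. One value capped at day 168.** With full follow-up this is R(168), a difference of 30.3. Suppose half of the losses follow week 6 and half follow week 12, unrelated to relapse. A teen lost after day c without use is credited with 168 days, so the expected value is R(c) + (168 − c)e^(−λc). In usual care this is 124.58 at c = 42 and 102.59 at c = 84, average 113.59, an excess of 113.59 − 90.89 = 22.7 days per lost teen.
- Null case, loss 15% PW/25% usual care: 0.10 × 22.7 = 2.3 days.
- Null case, loss 10%/30%: 0.20 × 22.7 = 4.5 days.
- Hazard ratio 0.5, 20% loss in both arms: 29.0 against a true 30.3.

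**4. Precision** (simulation, 3,000 trials, 25 per arm, no loss, hazard ratio 0.5). Capped mean: estimate 30.9, coverage 0.95, power 0.44, interval width 66.6. Kaplan-Meier restricted mean: 30.9, 0.95, 0.45, 65.3.

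**5. Loss related to relapse** (null, median 84, loss 10%/30%, every lost teen last seen at week 6 and relapsing before day 168). Here S(42) = 0.7071 and S(168) = 0.25, so 0.4571 relapse in between. After day 42 they average (90.89 − 35.49 − 0.25 × 126)/0.4571 = 52.3 days to relapse.
- Capping adds 126 − 52.3 = 73.7 days per lost teen: a shift of 0.20 × 73.7 = 14.7 days against PW.
- Kaplan-Meier, usual care: 35.49 + 0.7071 × (0.1571 × 52.3 + 31.5)/0.4071 = 104.5.
- Kaplan-Meier, PW: 35.49 + 0.7071 × (0.3571 × 52.3 + 31.5)/0.6071 = 93.9. The shift is 10.5 days.

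**6. Expected events among 50 teens** at hazard ratio 0.5, 25 × (2 − S₀(168) − S₁(168)): 42, 31, 20 and 11 for usual-care medians of 42, 84, 168 and 336 days.

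**The case against.** The discharge origin is an inference. Latency is listed beside two variables counted over the 90-day window, and on that reading each interview, including baseline, yields a value. This stands as a caveat on the mismatch, but it does not rescue the plan: the windows in step 1 do not measure a common quantity, and the text does not choose between the readings.

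A reader might infer that the plan would halve the effect, 14.6 against 30.3. The documents do not support that. The figure sets an average over three horizons against a single horizon, and the plan also intends to compare the arms at each time point. The week-24 contrast recovers 30.3. Pooling is possible under the wording but is not prescribed.

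A reader might also infer that abstinent teens would be dropped, which gives 9.2 days (74.4 − 65.2 among users only). No section proposes this, and it would conflict with the intent-to-treat statement.

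Finally, the simplest coding, one value capped at day 168, performs almost as well as Kaplan-Meier when loss is low or equal. Even with unequal loss unrelated to relapse, its shift is small against an interval about 65 days wide. Nor is Kaplan-Meier immune: step 5 shows that it moves too when loss depends on relapse, and the Missing data paragraph itself anticipates non-random dropout. All of this stands and limits the stakes.

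**Conclusion.** The point holds in a limited form. Latency is committed to analysis without an origin or a censoring rule. On the most natural reading, the one model prescribed for all outcomes does not fit it. The result then depends on an unstated choice: 3.1 to 30.3 days according to the visit used, 14.6 if pooled, and a shift of 2.3-4.5 days for a single capped value under unequal loss. These sizes rest on assumed exponential relapse, a median of 84 days and a hazard ratio of 0.5. The 2.3-4.5 also assumes loss unrelated to relapse.

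Practical harm is modest. This is a secondary, exploratory pilot outcome with power of about 45% in the central case, and hypothesis 2a names relapse rates rather than latency. This point does not touch use days, days abstinent or the Substance Frequency Scale. The change should still be made, because it replaces a model that does not fit with a standard one at little cost. Confidence that the text omits the definition is high; confidence in the specific mismatch is lower, because discharge is implied rather than stated.

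**What to change.** For this variable only, replace the mixed model and the own-baseline covariate.

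- **Definition.** Days from discharge to first use of each substance class, built by combining the follow-up calendars.
- **Censoring.** At the end of unbroken calendar coverage: normally the last completed interview, but day 42 if the 12-week interview is missed and the 24-week one is completed.
- **Analysis.** Kaplan-Meier curves by arm, with the restricted-mean difference to day 168 (or a Cox hazard ratio) and its 95% interval. Adjust for baseline days of use of that class and a small set of other covariates stated in advance.
- **Sensitivity.** Because loss may be informative, pre-state an analysis that counts lost teens as having used.
- **Hypothesis 2a.** Class-specific curves do not by themselves give its relapse rates, because relapse is not defined there. If the curves are to serve it, define relapse and add time to first use of any substance.

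The cost is SAP wording and one extra standard analysis on data already collected. The downside is that it serves a low-powered outcome. With about 20-42 events over the assumed medians of 168-42 days, and about 11 for a rarer substance (median 336), some covariates that the Data Analysis Plan says will be controlled may have to be left out of this model.

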The proposed study will evaluate one potential low cost, low intensity model for delivering parenting skills to parents preparing for their adolescent's discharge from residential substance use treatment. Specifically, this project will adapt the delivery of a computerized parenting intervention (Parenting Wisely; PW) that has preliminary evidence of efficacy in improving parenting skills and reducing youth behavior problems. PW delivery will be adapted for a new population (parents of ASUD preparing for discharge) and new setting (residential treatment), and preliminary data will be obtained on its feasibility, acceptability, and effectiveness. The open trial has been completed and consisted of recruitment, intervention, and assessment procedures with 10 parents to adapt the delivery of PW to include moderate engagement strategies relevant to this population. Initial engagement strategies have been developed based on focus groups and interviews with 13 parents, 11 ASUD, and three staff members and include up to four sessions of individualized coaching that begin prior to discharge (incorporated into standing family appointment times) and the use of technology (e.g., text messaging and an online parent message board) to maintain contact between staff and parents post-discharge.

Use of a low-cost, low-intensity intervention paired with moderate engagement strategies represents a marked change from traditional office-based treatment delivery methods. The approach has the potential to advance public health by: addressing a high-needs population; targeting parenting practices (putative mediators of change) that have been shown to influence ASUD outcomes; working with parents during a critical treatment juncture; improving parental engagement and access to care, and increasing ease of dissemination and implementation.

B. APPLICATION/PROPOSAL FOR FUNDING/SUPPORT

The initial grant awarded by the National Institutes on Drug Abuse proposed two phases – an open trial and a randomized controlled trial. This protocol pertains only to the **randomized control trial** portion of the study procedures proposed in the funding application at a new site.

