Please note the primary difference between the current proposal and the original application. In the original application, the target site was Gateway Residential Services (GRS). By the end of the study, the facility changed its name to the Caritas ARTS Program. In addition, we added a second site after consultation with the Project Officer, both to ensure we met the pre-specified recruitment target and to enable us to inform the design of a fully powered trial. The two programs are:

Caritas ARTS Program – short term residential facility with 16 beds, average length of stay 6-10 days

Rosecrance Health Network – long term residential facility with 80 beds, average length of stay 30-45 days

C. SPECIFIC AIMS AND DETAILED STUDY METHODOLOGY

1. Specific Aims

The goal of this pilot study is to adapt the delivery of PW for a new population (parents of ASUD preparing for discharge) and new setting (residential treatment), and to obtain initial data on its feasibility, acceptability, and effectiveness. The study began with an open trial of 10 parents to demonstrate feasibility, acceptability, and preliminary evidence of effectiveness over time.

Specific research aims of the protocol are:

Aim 1: To examine the feasibility and acceptability of an adapted PW intervention that includes moderate engagement strategies for parents of ASUD preparing for discharge from residential.

Hypothesis 1a: Adapted PW will be both feasible and acceptable to parents. Feasibility will be indicated by enrollment rates ($\geq 80\%$) and indicators of parent engagement: attendance of ≥ 2 coaching sessions for $\geq 75\%$ of parents, and online usage patterns of 2+ PW logins, viewing of video vignettes embed in text messages, 1+ parent board posts. Criteria for acceptability will be withdrawal rates ($\leq 20\%$), $\geq 80\%$ of ratings on a consumer satisfaction scale in the highest two categories, and positive feedback from exit interviews with parents.

Secondary Aims 2-4: To examine the preliminary effectiveness of the experimental intervention on: substance use outcomes, related high-risk behaviors, and parenting skills (the putative mediators of change).

Hypotheses: At baseline, 6-week follow up, 12-week follow up, and 24-week follow-up, the experimental intervention will demonstrate superior outcomes, relative to treatment as usual on:

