Individual Coaching Sessions. Individual coaching sessions are designed to individually tailor the PW skills to each parent's presenting concerns. Parents may receive up to 4 sessions by the first follow-up assessment (scheduled 6 weeks post discharge). Based on PI [name]'s consultation with PW developer Consultant [name], we have selected 4 core parenting skills to emphasize in the sessions: I-statements, Contracting, Active Listening, Reframing. The initial session will be 60-75 minutes and will consist of several sections: 1) Rationale for parenting skills, 2) Review of feedback from the baseline in vivo parent-adolescent interaction task in order to cater the computerized parenting program to the families' specific needs 3) Overview of four core parenting skills; 4) Review of PW substance use module, and 5) practice applying the skill to a current problem. Subsequent sessions will be 45-60 minutes and will follow the same basic outline, while introducing the remaining core skills. When parents have questions or introduce problems/complaints about their teen, the coach will first provide validation and then discuss how the parents' problems can be addressed using a skill. Parents will be offered sessions remotely via phone or video-conference technology.

Text-based messaging. Immediately upon enrollment in the PW condition, parents will receive daily text messages for 6 months to reinforce skills from PW, to motivate continued participation in PW, and to encourage participation in the online parent message board (described below). Parents will be able to choose if they want to receive the text messages in English or Spanish. Approximately half of the texts reinforce material taught in PW, along with a link to a video clip enacting a core PW skill. For example, a message might contain a simple reminder statement about a parenting strategy such as limit- setting, monitoring, and communication with a link to a video clip demonstrating this strategy. The second half of all text messages either offer an encouragement for the parent to complete more PW sections or an encouragement to

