
THERAPIST TRAINING / SUPERVISION.

Treatment will be delivered by Bachelor's or Master's-level parent coaches from the Brown University research team, one of whom is bilingual in English and Spanish.. All therapists will be trained to demonstrate sufficient adherence and competence by PI [name]. As a first training step, therapists will be required to review the manual, PW workbook, and modules of the PW computerized intervention. The PI and two therapists will then role-play and videotape the 4 core sessions. PI [name] will view these role plays, complete measures of therapist adherence and competence, and provide brief written summaries. Competency will be rated with 6 items that comprise the "General Therapeutic Skills" section of the Cognitive Therapy Rating Scale (CTRS), which is routinely used to assess therapist competence in Co-I [name]'s protocols. The CTRS is well suited to assess the in-person coaching sessions, since these sessions use a structured, skills- based, and collaborative approach. A score ≥ 24 is the

criterion to indicate competence on the 6 item version. PI [name] will calculate a consensus CTRS score and provide a synthesis of written feedback to each therapist. Adherence measures will be developed in collaboration with Consultant [name] based on the in-person manual. Therapists will be required to earn a satisfactory consensus CTRS score of ≥ 24 on 3 of 4 role plays and satisfactory adherence ratings to be assigned a participant.

Once the Brown therapists are assigned participants, sessions will be audio recorded and rated for competence and adherence. PI [name] will review and rate the first two tapes for adherence and competence. If ratings are satisfactory, PI [name] and the post-doctoral fellow will collectively review 25% of tapes (i.e., 1 of the 4 remote sessions per client) moving forward. PI [name] will meet weekly with therapists for supervision focused on adherence to the protocol, therapist skill in protocol delivery, and how to tailor the PW protocol to each parent's unique presenting concerns.

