FAsTask Video Code. The FAsTask is an interactive family problem solving task that will be used to provide an in-vivo assessment of parenting behaviors. We have limited the assessment to three tasks that align with our primary aims: 1) Limit Setting (parent leads a 5 min discussion about a time they had to set a limit); 2) Substance Use Norms (parent leads a 5 min discussion on family views about substance use); and 3) Monitoring and Listening (teen leads a 5 min discussion on their peers and parent listens and reacts). Co-I [name] has created a structured clinical codebook that defines each item to be coded and gives specific examples of high and low-scoring observations. Interactions will be observed during each phone or video conference assessment and will be audio recorded. Tapes will be coded by raters blind to condition: 20% of tapes will be double coded.

Data Analysis Plan.

All 60 parents will be included in statistical analyses consistent with an intent-to-treat (ITT) model. Prior to the main analyses, we will run descriptive statistics on key variables to examine distributional properties, identify outliers, and transform variables as needed. The two treatment conditions will be compared on all baseline demographic and clinical variables. Pre-existing differences on any variables and any additional treatment received will be controlled in subsequent analyses.

Missing data. GAIN data is entered into the GAIN's proprietary software, which offers instant error checks and validation reports to prevent missing data. Other forms will be entered directly into study laptops using REDCap (Research Electronic Data Capture), a secure web-based application, to reduce missing data and entry errors. Attrition analyses will compare follow-up completers and non-completers on baseline clinical and demographic variables to determine if they differ systematically. If necessary, we will use standard methods of multiple imputation [123] for variables where unplanned missingness is an issue. For each follow-up time point, we will conduct analyses to identify systematic biases that may have arisen due to non-random dropout.

Aim 1. In the RCT, feasibility will be examined via enrollment rates ($\geq 80\%$) and indicators of engagement, with these preliminary targets: attendance of ≥ 3 of 4 coaching sessions pre-

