discharge and ≥ 1 of 2 sessions post-discharge for $\geq 75\%$ of parents, and online usage patterns of 3+ PW logins, 2+ parent board logins, and 2+ hours logged in for $\geq 75\%$ of parents. Criteria for acceptability include withdrawal rates ($< 20\%$), satisfaction ratings ($\geq 80\%$ of CSQ items rated “agree” or “strongly agree”) and positive feedback from the exit interviews with parents and therapists. Criteria will be finalized based on parent and staff feedback in Phase 1.

Aims 2 - 4. The dependent variables (DVs) include substance use (Aim 2), related high-risk behaviors (Aim 3), and parental monitoring and communication (Aim 4, putative mediators). By nature of residential treatment, we expect teens’ level of substance use and risk behavior to start high at intake, drop off for the duration (~ 3.5 months) of treatment and then increase over the follow-up period. Trajectories that begin at baseline would be misleading, since all teens will have a sustained period of abstinence (with minimal variance). We therefore compare trajectories of use over the follow-up period, while controlling for baseline status as covariates.

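### Aim 1 has two unreconciled sets of feasibility criteria, and the set in the analysis plan counts six coaching sessions where the protocol offers at most four

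*Combined protocol and SAP*

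**What the plan says.** **Hypothesis 1a (Section C.1, Specific Aims)** sets the coaching target as "attendance of ≥ 2 coaching sessions for" at least 75% of parents. It adds "online usage patterns of 2+ PW logins, viewing of video vignettes embed in text messages, 1+ parent board posts". Vignette viewing has no count, and no percentage of parents is clearly attached to the online items.

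**Data Analysis Plan, Aim 1** says feasibility in the RCT is examined by "attendance of ≥ 3 of 4 coaching sessions pre"-discharge and "≥ 1 of 2 sessions post-discharge" for at least 75% of parents, with "online usage patterns of 3+ PW logins, 2+ parent board logins, and 2+ hours logged in", again for at least 75%. It labels these targets preliminary and says the criteria are to be finalised from Phase 1 feedback.

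**Number of sessions offered.** The project summary describes "up to four sessions of individualized coaching that begin prior to discharge". Individual Coaching Sessions states: "Parents may receive up to 4 sessions by the first follow-up assessment (scheduled 6 weeks post discharge". Therapist Training / Supervision equates its 25% tape review with "1 of the 4 remote sessions per client". The Acceptability measures also count four.

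**Status of Phase 1.** The protocol describes two phases, an open trial and the RCT, and says the open trial is complete. No section says which set of criteria came out of it.

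**The concern.** Aim 1 is listed first, and the Specific Aims section labels Aims 2-4 secondary (although the Aims 2-4 analysis text calls the Aims 2-3 measures primary outcomes). Sample Size, Power, and R01 treats high feasibility and acceptability, paired with a small to medium effect size, as the indication for a larger trial, and it names no threshold set. With two sets in force, the same attendance and login data can be reported as meeting or missing the target, and the choice could be made after the data are seen.

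The analysis-plan attendance rule also does not fit the intervention as described, because it counts sessions that the protocol does not offer.

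**Working it through.** **1. Session count.** The analysis-plan denominators are 4 before and 2 after discharge: 4 + 2 = 6. Elsewhere the maximum is 4.

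**2. Can the rule be met with four sessions?** The (pre, post) attendance pairs that satisfy at least 3 of 4 and at least 1 of 2 are (3,1), (3,2), (4,1) and (4,2). Only (3,1) totals four or fewer. The rule can be scored, because the Feasibility measures count sessions before and after discharge separately, but only one attendance pattern passes.

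**3. Online criteria side by side.** Neither set contains the other.
- A parent with 3 PW logins, 2 board logins, 2 hours and no post meets the analysis plan and fails Hypothesis 1a.
- A parent with 2 PW logins, vignettes viewed and 1 post meets Hypothesis 1a and fails the analysis plan.

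**4. Result without modelling.** If every parent attends exactly two sessions, Hypothesis 1a is met by 100% and the analysis-plan rule by 0%.

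**5. Illustration on four sessions.** Assumptions not in the documents: 1:1 allocation of the 60 dyads, so 30 intervention parents; three sessions before and one after discharge; independent attendance with probability p per session. Since 0.75 × 30 = 22.5, the target is at least 23 of 30.
- Hypothesis 1a share = P(Bin(4, p) ≥ 2)
- Analysis-plan share = p⁴ (all four attended)

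| p | Share, H1a | Share, analysis plan | P(≥ 23/30), H1a | P(≥ 23/30), analysis plan |
|---|---|---|---|---|
| 0.60 | 0.821 | 0.130 | 0.845 | <0.001 |
| 0.70 | 0.916 | 0.240 | 0.997 | <0.001 |
| 0.80 | 0.973 | 0.410 | >0.999 | <0.001 |
| 0.90 | 0.996 | 0.656 | >0.999 | 0.138 |
| 0.95 | 0.9995 | 0.815 | >0.999 | 0.821 |

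For an expected 75% of parents to qualify, p must be 0.544 under Hypothesis 1a and 0.75^(1/4) = 0.931 under the analysis plan.

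**6. Attendance correlated within parent.** Beta-binomial with correlation 0.5, so a + b = 1/0.5 − 1 = 1. At mean 0.8 (a = 0.8, b = 0.2), the analysis-plan share is 0.8 × 1.8 × 2.8 × 3.8 / 24 = 0.638 and the Hypothesis 1a share is 0.859; P(≥ 23/30) is 0.099 against 0.949. At mean 0.9 the shares are 0.806 and 0.936; P is 0.786 against 0.9995.

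**7. If six sessions were offered (4 before, 2 after).** Hypothesis 1a share = P(Bin(6, p) ≥ 2). Analysis-plan share = P(Bin(4, p) ≥ 3) × P(Bin(2, p) ≥ 1).

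| p | Share, H1a | Share, analysis plan | P(≥ 23/30), H1a | P(≥ 23/30), analysis plan |
|---|---|---|---|---|
| 0.70 | 0.989 | 0.593 | >0.999 | 0.037 |
| 0.80 | 0.998 | 0.786 | >0.999 | 0.698 |
| 0.90 | >0.999 | 0.938 | >0.999 | >0.999 |

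**8. Acceptability.** Withdrawal is at most 20% in one set and under 20% in the other, which differ only at exactly 20%. Satisfaction is defined by the top two categories in one set and by two agreement labels in the other. The questionnaire is described as a 7-point scale without labels, so the text does not show whether these are the same.

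**The case against.** The best defence is that the plan marks its own set as provisional. Hypothesis 1a carries no such label, fits four sessions and refers to the text-message vignettes, so it may be the finalised set and the analysis-plan text a carry-over. The treatment duration of about 3.5 months in the Aims 2-4 analysis text, which matches neither site's length of stay, points the same way. This is plausible, but no sentence says so, and the analysis plan still prescribes its own figures for the RCT. Finalisation was tied to a phase that the protocol reports as complete, so a final set should now be named.

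It can also be said that this is a pilot with no mechanical go/no-go rule, that the conflict affects no randomisation, effect estimate or safety rule, and that either set can largely be scored from the data collected. All of that is true and limits the damage to Aim 1. It does not tell a reader whether Aim 1 was met.

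Finally, the widest gaps come from scoring a rule written for six sessions on four, under assumed attendance rates. That stands as a caution: with six sessions the gap is smaller at p = 0.8 and gone at p = 0.9. The contradiction itself needs no model.

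**Conclusion.** The concern holds and must be fixed. Two different sets of Aim 1 criteria stand in current text with nothing to say which governs, and the analysis-plan set counts six sessions against a stated maximum of four. Under that maximum, full attendance before discharge counts as failure.

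The choice of set can turn the verdict from 100% to 0% on identical data. In the four-session illustration it decides the outcome for per-session attendance from 0.6 to 0.9; by 0.95 the analysis-plan rule would also probably be met (0.82). Those figures rest on 30 intervention parents, a 3/1 split and the assumed attendance model. The session count and the conflict between the sets rest on the text alone.

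The sets do agree on enrolment (at least 80%) and on 75% as the share of parents for coaching.

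**What to change.** Before Aim 1 outcome data are reviewed, name one governing, dated set of criteria and delete the other. If the data have already been seen, state which set was in force and from when. In that set:

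- Write attendance as at least k of the N sessions the protocol offers, with 75% of parents randomised to the intervention as the target.
- State the share of parents that each online item must reach, and give vignette viewing a count or remove it.
- Use one withdrawal cut-off and one satisfaction definition tied to the 7-point scale.
- Report each rate with an exact 95% confidence interval; 23/30, for example, gives 58% to 90%.

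Hypothesis 1a is one candidate because its attendance rule fits four sessions, but the sponsor must choose.

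Separately, the statements on session number and timing in Randomization, Individual Coaching Sessions and the Aim 1 analysis must be reconciled with each other and with the sites' lengths of stay. A first session about 4 weeks before discharge is compatible with the 30-45 day site but not with the 6-10 day site. The 3.5-month duration matches neither.

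The cost is protocol and SAP wording. Session, login, posting and time counts are already listed among the Feasibility measures; vignette viewing is not. The sponsor gives up the option of reporting against either set.
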